# 7.2.1.4 Vital Signs (Blood Pressure, Pulse Rate, and Body Temperature)

Systolic and diastolic blood pressures, pulse rate, and body temperature will be measured at rest according to the procedures specified by the trial site, and the date of evaluation and the result will be recorded in the source documents and CRF. In case if abnormal values are not judged as AEs, enter the reason in source documents.

# 7.2.1.5 12-Lead Electrocardiogram

Measure 12-lead ECG parameters according to the procedures of the trial site with paper feed speed at 25 mm/sec.

The investigator or subinvestigator will record the date of measurement and presence/absence of abnormality in the source documents and CRF. In case if abnormal findings are not judged as AEs, enter the reason in source documents.

The sponsor will retrieve copies of all the ECG charts.

# 7.2.1.6 Confirmation of Investigational Medicinal Product Compliance Status and Food

The investigator or subinvestigator will distribute patient diary to have them record the information on the compliance with IMP and food intake during the administration period. Based on the information recorded in the patient diary, the investigator or subinvestigator will record in the CRF the patient's IMP compliance during the administration period,

whether or not the IMP was taken after meals, and the time of day that the IMP was taken on the day of blood sampling for PK assessment.

## 7.2.2 Efficacy Evaluation

# 7.2.2.1 Microbiological Outcome

#### 1) Timing

CDI group: screening, Day 4, Day 11 (end of treatment), at FU2 (Day 38), at the time of withdrawal

Enteric infection group: screening, Day 4, Day 8 (end of treatment), at the time of withdrawal

#### 2) Method of Examination

Collect approximately 3 g of stool from the patient using the stool sample container provided by the microbiological laboratory. The containers will be labeled with the study number, patient number, and sampling day. Collect stool specimens within 48 hours prior to IMP administration for the screening time point and within 24 hours before the observation day for other time points. Store stool samples at approximately 4°C until a designated courier collects them.

The microbiological laboratory will follow the predetermined procedures and perform the culture and identification by centralized measurement. The isolated strains will be stored in order to enable exploratory investigation in the future on the bacteriological and genetic characteristics other than drug sensitivity of the isolated strains.

If the result of measurement requires notification in line with the Infectious Diseases Control Law, each trial site will submit notification in accordance with relevant laws, regulations, and notifications of each country.

#### 3) Method of Evaluation

The investigator or subinvestigator will identify the causative pathogen on the basis of the microbiological examination results from the microbiological laboratory and record sampling date, the causative pathogen, and pathogen culture results in source documents and CRF. If there is more than one possible causative pathogen, identify all causative pathogens and record the pathogen culture results by causative pathogen in source documents and CRF. The sponsor will collect the microbiological examination results from the microbiological laboratory and judge microbiological outcome by bacterial strain isolated as the causative pathogen based on the change in microbiological examination results according to the assessment criteria shown in Table 3.3-1 and Table

3.3-2. For infection due to multiple causative pathogens, microbiological outcome will be assessed for each individual pathogen.

## 7.2.2.2 Toxin A/B Assay

#### 1) Timing

CDI group: screening, Day 4, Day 11 (end of treatment), at FU2 (Day 38), at the time of withdrawal

#### 2) Method of Examination

At screening, perform toxin A/B assay according to the procedures specified by the trial site for assessing eligibility on the basis of the test result at the trial site (when PCR and colonoscopy were performed, toxin A/B assay at the trial site is not indispensable). Record the sampling date and the test result in source documents.

At all scheduled time points, including screening, toxin A/B assay will be centrally performed by the microbiological laboratory using the stool specimens for the assessment of microbiological outcome. The microbiological laboratory will perform toxin A/B assay and report the result to the investigator or subinvestigator. (Note: For the enteric infection group, in order to assess patient eligibility, the toxin A/B assay or PCR at screening is also to be performed at the trial site according to the procedure specified by the trial site. Record the sampling date and the test result in source documents.)

### 3) Method of Evaluation

The investigator or subinvestigator will record the sampling date in source documents and CRF. The sponsor will collect the toxin A/B assay result only of the CDI group tested at the microbiological laboratory. Use the result of toxin A/B assay from the microbiological laboratory.

#### 7.2.2.3 Clinical Response

## 1) Timing

CDI group: Day 4, Day 11 (end of treatment), at the time of withdrawal

Enteric infection group: Day 4, Day 8 (end of treatment), at the time of withdrawal

## 2) Method of Evaluation

The investigator or subinvestigator will refer to the information from patients (eg, patient diary), and assess clinical response at the time of observation (Day 4 and end of treatment) according to the assessment criteria shown in Table 3.3-3. The investigator or subinvestigator will record the assessment date and result in source documents and CRF.

# 7.2.2.4 Recurrence of *Clostridium Difficile* Infection (*Clostridium Difficile* Infection Group Only)

1) Timing

CDI group: at FU2 (Day 38), at the time of withdrawal

#### 2) Method of Confirmation

The investigator or subinvestigator will assess the recurrence of CDI at FU2 or withdrawal according to the assessment criteria shown in Table 3.3-3 for patients who achieved "clinical cure" at the end of treatment. The investigator or subinvestigator will record the assessment date and result in source documents and CRF.

#### 7.2.2.5 Time to Resolution of Diarrhea

The sponsor will evaluate the time from the start of dosing until the first formed stool (except in cases where liquid or unformed stools recur), as the time to resolution of diarrhea on the basis of the record of fecal properties in CRF obtained according to the procedure of 7.2.2.6.

## 7.2.2.6 Improvement of Clinical Symptoms

1) Timing

CDI group: Day 4, Day 11 (end of treatment), at FU2 (Day 38), at the time of withdrawal

Enteric infection group: Day 4, Day 8 (end of treatment), at the time of withdrawal

#### 2) Method

Distribute patient diary to patients and have the patients to record daily stool count, fecal properties, presence/absence of bloody stool, highest body temperature, and presence/absence of abdominal pain, nausea, and vomiting. If the patient is not able to record the information in the patient diary on his/her own, medical personnel or the patient's family will record the information in the diary on behalf of the patient.

#### 3) Method of Evaluation

The investigator or subinvestigator will record the information on the patient diary in CRF. The sponsor will evaluate the change in improvement of clinical symptoms by comparing the record of daily stool count, fecal properties, bloody stool, fever, abdominal pain, nausea, and vomiting described in CRF with those at pre-treatment.

## 7.2.2.7 Drug Sensitivity of Isolated Strain

1) Timing

CDI group: screening, Day 11 (end of treatment), FU2 (Day 38)

Enteric infection group: screening, Day 8 (end of treatment)

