# 3.3.2.4 Recurrence of *Clostridium Difficile* Infection (*Clostridium Difficile* Infection Group Only)

The investigator or subinvestigator will assess the recurrence of CDI at FU2 or withdrawal according to the assessment criteria shown in Table 3.3-4 for patients who achieved "clinical cure" at the end of treatment.

Table 3.3-4 Assessment Criteria for Recurrence of *Clostridium Difficile* Infection

Assessment of Recurrence of CDI	Definition
Sustained cure	No recurrence
Recurrence	
 
Meeting all the following criteria
 
New episode of diarrhea is occurred in the period from the end of treatment to FU2 or withdrawal (liquid or unformed stools ≥ 3 times/day within 24 hours)
 

	Medication or therapy is required to treat CDI in the period from the end of treatment to FU2 or withdrawal
	A positive toxin A/B assay at FU2 or withdrawal (positive for either or both toxins)

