#### 9.2 Criteria and Procedures for Withdrawal of Individual Patients

In any of the events listed below, the investigator or subinvestigator will discontinue IMP administration, perform the tests to be performed at withdrawal stipulated in Section 7.1, Schedule and Procedures of the Trial, and promptly inform the sponsor of the withdrawal (Annex, Emergency Contact). The investigator or subinvestigator will record the date and reason for withdrawal in the source documents and CRF.

If withdrawal is necessitated by problems with safety, such as the occurrence of an AE or aggravation of the underlying disease, the investigator or subinvestigator will promptly take appropriate measures and perform follow-up if necessary (refer to Section 8.4 Follow-up Investigation of Adverse Events).

- 1. If the patient wishes to withdraw
- 2. If it is found after the start of the trial that the patient did not meet all the inclusion criteria or fell under any of the exclusion criteria
- 3. If a drug or therapy from either item 1 or item 7 in the list of prohibited concomitant drugs and therapies is used or judged to be required
- 4. If an AE making continuation of trial participation difficult occurs
- 5. If the female patient is found to be pregnant
- 6. If symptoms of the primary disease exacerbate, and the investigator or subinvestigator judges that it is not appropriate to continue the trial participation
- 7. If it becomes impossible to comply with the protocol for any another reason or if the investigator or subinvestigator judges that it is necessary to discontinue the trial participation for any another reason

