# 11.3.4.7 Drug Sensitivity of Isolated Strain

1) Endpoint

MIC values

2) Analysis Set

C. difficile isolated/identified or the strain identified as enteric infection agents by the microbiological laboratory

3) Analysis Method

Prepare a list of kinds and number of strains of the identified causative strain. Determine MIC value of OPS-2071 for the causative strain at screening and at the end of treatment (and FU2 [Day 38] for CDI group) to prepare a list.

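### Isolates grown at the withdrawal examination have no scheduled MIC, so the post-baseline sensitivity list under-represents patients with poor outcomes

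*Protocol*

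**What the plan says.** The sensitivity of the causative strain to OPS-2071 is a secondary objective (protocol section 2). Section 7.2.2.7 sets the test times: "CDI group: screening, Day 11 (end of treatment), FU2 (Day 38"), and "Enteric infection group: screening, Day 8 (end of treatment"). The analysis in 11.3.4.7 matches: "Determine MIC value of OPS-2071 for the causative strain at screening and at the end of treatment (and FU2 [Day 38] for CDI group"). In Table 7-1 the sensitivity rows are blank in the withdrawal column for both disease groups. The withdrawal lists in 7.1.7.1 and 7.1.7.2 do not name the test.

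Culture follows a different schedule. For the CDI group, 7.2.2.1 gives: "CDI group: screening, Day 4, Day 11 (end of treatment), at FU2 (Day 38), at the time of withdrawal". For the enteric infection group, 7.1.7.2 orders a withdrawal culture only if the patient leaves during dosing.

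Section 9.2, criterion 3, requires withdrawal: "If a drug or therapy from either item 1 or item 7 in the list of prohibited concomitant drugs and therapies is used" or is judged necessary. Item 7 in 6.2.1 covers other treatments for CDI and enteric infection and applies to the end of the trial. Table 3.3-4 makes this one of the conditions that must all be met for a recurrence: "Medication or therapy is required to treat CDI in the period from the end of treatment to FU2 or withdrawal".

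**The concern.** The visits with an MIC are those reached by patients who stay in the trial. Patients who need other therapy are directed to the one examination at which a strain may be grown but its MIC is not determined. Whether an isolate is tested then depends in part on how the patient fared.

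An MIC after baseline is of interest mainly because it can be set against the baseline value. Section 1.2.1.1 presents a low presumed risk of emerging resistance as a feature of the drug, so readers are likely to look at the list in that light. If isolates from withdrawn patients are missing, a list without raised MICs is weaker evidence than it appears. With about 10 CDI patients per dose, one or two missing isolates would be a noticeable share of the informative ones.

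**Working it through.** The protocol states no figure for this point, so the check is mainly a comparison of schedules.

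**1. Culture against MIC, by visit**

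| Visit | CDI: culture | CDI: MIC | Enteric: culture | Enteric: MIC |
|---|---|---|---|---|
| Screening | yes | yes | yes | yes |
| Day 4 | yes | no | yes | no |
| End of treatment (Day 11 / Day 8) | yes | yes | yes | yes |
| FU2 (Day 38) | yes | yes | no such visit | no such visit |
| Withdrawal during dosing | yes | **no** | yes | **no** |
| Withdrawal after dosing | yes | **no** | no | no |

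Sources: Table 7-1, 7.1.2, 7.1.5 to 7.1.7, 7.2.2.1, 7.2.2.7 and 11.3.4.7. These places agree with each other, so this is a consistent gap and not a contradiction. Day 4 isolates are not tested either, so a patient withdrawn during dosing has no scheduled post-baseline MIC at all.

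**2. Who reaches the withdrawal examination**

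- During dosing, in both groups: patients who need other therapy (criterion 3) or whose disease worsens so that the investigator ends participation (criterion 6), along with those leaving for unrelated reasons.
- After dosing, in the CDI group: a recurrence requires that CDI therapy is needed (Table 3.3-4). That need meets criterion 3. A recurrence recognised before FU2 therefore leads to withdrawal. Section 7.1.7.1 anticipates this by scheduling the recurrence assessment at withdrawal after dosing.

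**3. Whether there would be material to test**

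Table 3.3-4 also requires a positive toxin assay at FU2 or withdrawal. Under 7.2.2.2 the microbiological laboratory runs that assay on the stool collected for microbiological outcome. A recurrence counted at withdrawal therefore has a stool sample at the laboratory that also does the cultures. Whether a strain grows from it is not known in advance.

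**4. Whether storage fills the gap**

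Section 7.2.2.1 says: "The isolated strains will be stored in order to enable exploratory investigation in the future", but limits this to characteristics other than drug sensitivity. Storage alone does not produce the missing MICs.

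**5. Illustrative size, CDI recurrences**

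Inputs: 3 doses × 10 CDI patients = 30 (section 3.4), and recurrence of 15% to 30% for existing drugs (section 3.2). Assumptions: all 30 are cured, and OPS-2071 has the same recurrence rate.

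- Expected recurrences: 30 × 0.15 = 4.5 to 30 × 0.30 = 9.
- Per dose: 10 × 0.15 = 1.5 to 10 × 0.30 = 3.
- Recurrence isolates without an MIC = expected recurrences × share recognised before FU2 × share growing on culture.

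The documents give neither share. Under these assumptions the expected number of untested recurrence isolates can lie anywhere from 0 to 9. Isolates from withdrawals during dosing would add to it, and no rate is given for those.

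**The case against.** The strongest reply is that the isolates that matter most are tested. The sensitivity test at Day 11 or Day 8 covers everyone who attends with a strain, whatever the clinical outcome. A patient who completes the course and fails, or is still culture positive, gets an MIC. A recurrence first found at FU2 is tested too. Recurrence is judged only in patients cured at the end of treatment, and cure has no culture criterion, so some patients who later recur may already have a Day 11 MIC. All of this stands. A reader might infer that resistant isolates are never tested, or that the list contains only patients who did not fail. The documents do not support either reading.

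A reader might also infer that nearly all recurrences would go without an MIC. That has no source either, because the protocol is silent on their timing and culture yield.

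It can also be said that the objective concerns the sensitivity of isolated strains, which screening isolates serve, and that 11.3.4.7 plans a listing with no claim about change in MIC. That is correct and limits the weight of the point. It does not explain why the protocol repeats the test at the end of treatment and FU2 but omits it at the other post-baseline examination tied to outcome.

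Finally, 7.1.7 accepts that some withdrawal tests may not be possible, and names CDI recurrence as an example. Some patients will give no isolate, which lowers the yield of the fix without removing the reason for it.

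**Conclusion.** The point holds in limited form. Culture-positive isolates from withdrawals during dosing (both groups) and after dosing (CDI group, including recurrences needing therapy before FU2) have no scheduled MIC. The post-baseline list therefore under-represents patients with poor outcomes, and the FU2 list does so most.

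The size cannot be fixed from the protocol. The 4.5 to 9 recurrences are an illustration resting on cure in all 30 CDI patients and on a rate cited for other drugs; only those occurring before FU2 and growing on culture would be affected. Enteric infection patients who withdraw after dosing have no culture, so they have no isolate to test.

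This is an inexpensive improvement to a descriptive secondary endpoint, not an error that undermines the trial. A statistical analysis plan cannot repair it, because it cannot list MICs that the schedule does not generate.

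**What to change.** Add the drug sensitivity test, on any causative strain grown from the withdrawal culture, to:

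- the withdrawal column of Table 7-1, for both disease groups;
- 7.1.7.1 (CDI group);
- 7.1.7.2 (enteric infection group, withdrawal during dosing only, where culture is already done);
- the timing in 7.2.2.7;
- the time points in 11.3.4.7.

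In 11.3.4.7, also list each patient's baseline and last MIC beside the clinical outcome, so that missing post-baseline values can be seen against outcome.

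The cost is amendment wording and a small number of extra MIC determinations by the microbiological laboratory that already cultures these samples. No visit, stool sample or clinical rule changes.

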#### 2) Method of Examination

The microbiological laboratory will determine the MIC of OPS-2071 for the isolated/identified *C. difficile* or the strain identified as the causative pathogen of enteric infection. On the basis of the procedures specified by the microbiological laboratory, assess drug sensitivity.

#### 3) Method of Evaluation

The investigator or subinvestigator will record the sampling date in the source documents and CRF. The sponsor will collect the result of drug sensitivity test on isolated strains determined in the microbiological laboratory.

#### 7.2.3 Pharmacokinetic Evaluation

#### 7.2.3.1 Plasma Pharmacokinetics

### 1) Timing

Inpatient: 1 ( $\pm$  15 minutes), 2 ( $\pm$  15 minutes), and 4 ( $\pm$  30 minutes) hours after morning administration on Day 4

Outpatient: Once within 12 hours after morning administration but before evening administration on Day 4

#### 2) Method

A volume of approximately 5 mL whole blood will be collected into a lithium heparincontaining blood collection tube. Samples will be immediately placed on crushed ice and centrifuged (2000 g for 15 minutes at 4°C) within 1 hour of collection to obtain plasma. Two aliquots of 700  $\mu$ L plasma will be transferred to two polypropylene tubes and stored approximately at -80°C. The plasma samples will be labeled with the following information: study number, patient number, sampling day and time point, and aliquot type (primary or back-up).

Record sampling day and time point, and date and time of latest medication in the source documents and CRF.

# 3) Shipment of Samples

Samples will be shipped on dry ice by a designated courier to laboratory performing measurement of drug concentrations (hereafter, bioanalytical laboratory). Back-up samples will be separately sent to the bioanalytical laboratory.

#### 4) Method of Determination

Plasma concentrations of OPS-2071 will be determined using a validated liquid chromatography—tandem mass spectrometry (LC-MS/MS) method by the bioanalytical laboratory.

The bioanalytical laboratory will submit a report on the result of drug concentration measurements to the sponsor. The report submitted to the sponsor is considered as the source documents. Record in the CRF will not be required. Remaining samples after measurement of drug concentrations will be stored approximately at  $-80^{\circ}$ C in the bioanalytical laboratory until the completion of clinical study report. After the completion of clinical study report, the bioanalytical laboratory will promptly discard the remaining samples and record it.

# 7.3 Measures to Be Taken for Patients Visiting or Planning to Visit Other Hospitals or Departments

At the time of obtaining informed consent, the investigator or subinvestigator will confirm whether or not the patient is receiving treatment at another hospital or department. If the patient is receiving treatment at another hospital or department, the investigator or subinvestigator will inform the attending physician of that hospital or department about the patient's participation in the clinical trial and the IMP being used, with the patient's consent. The investigator or subinvestigator will also obtain and record in source documents and the CRF information on the treatment that the patient is receiving at the other hospital or department (name of disease being treated and information on the type of treatment or measures being implemented) and judge whether or not the patient should participate in the trial.

If a patient visits another hospital or department during the trial period, the investigator or subinvestigator will inform the attending physician of that hospital or department about the patient's participation in the clinical trial and the IMP being used, with the patient's consent. The investigator or subinvestigator will also obtain and record in source documents and the CRF information on the treatment that the patient receives at the other hospital or department (name of disease treated and information on the type of treatment or measures implemented) and judge whether or not the patient should continue to participate in the trial.

## 8 Adverse Events

#### 8.1 Definitions

#### 8.1.1 Adverse Event

An AE is any untoward medical occurrence in a patient or clinical investigation patient administered a pharmaceutical product and which does not necessarily have to have a causal relationship with this treatment.

An AE can therefore be any unfavorable and unintended sign (including an abnormal laboratory finding, for example), symptom, or disease temporally associated with the use of an IMP, whether or not considered related to the IMPnotes)

For this trial, OPS-2071 is regarded as the IMP, and to secure the safety of patients, AEs occurring from the time of signing the ICF to the start of OPS-2071 administration are included in the definition of AEs in addition to the definition given by ICH.

If an event, symptom, or sign existing at the time of acquisition of informed consent worsens after acquisition of informed consent, or if an AE occurring between the acquisition of informed consent and start of OPS-2071 administration worsens after administration of OPS-2071, the exacerbation will be treated as a new AE.

